8.8 Safety Oversight

This study will be overseen by the BPCA DMC, the NICHHD, and the FDA. The DMC will review data from individual study participants on a quarterly basis to evaluate the progress of the study and the safety and confidentiality of study participants. This evaluation will also assess data quality and timeliness, participant recruitment, accrual, and retention. These reviews will allow the DMC to determine whether there is any change to the anticipated benefit-to-risk ratio of study participation. These reviews will also allow the DMC to determine whether the study should: 1) continue as originally designed, 2) implement a protocol change, or 3) be terminated. If a recommendation is made to change the research study design, an adequate rationale for this decision must be provided.

Ad Hoc Meetings of the DMC: The DMC may convene an ad hoc meeting to discuss any issue of safety raised by an investigator, the IND sponsor, or a member of the DMC. At the discretion of the investigators, the sponsor, and DMC members, a non-serious AE that is 1) associated with the product and 2) does not meet the stopping rules criteria may be considered as a trigger for an ad hoc DMC meeting to assess the safety of the product, without resulting in halting the enrollment of the trial.

9 CLINICAL MONITORING

Site monitoring will be conducted to ensure that human subject protection, study procedures, laboratory procedures, study intervention administration, and data collection processes are of high quality and meet sponsor, GCP/ICH, and regulatory guidelines, and that the study is conducted in accordance with the protocol and DCC or Duke Clinical Research Institute (DCRI) sponsor standard operating procedures. The IND sponsor, or as detailed in the Transfer of Regulatory Obligations, the DCC, NIH/NICHHD, or its designee will conduct site-monitoring visits as detailed in the monitoring plan. Site visits will be made at standard intervals as defined by the clinical monitoring plans and may be made more frequently as directed by the IND and funding sponsors. Monitoring visits will include, but are not limited to, review of regulatory files, accountability records, CRFs, informed consent forms, medical and laboratory reports, and protocol compliance. Study monitors will meet with investigators to discuss any problems and actions to be taken and document visit findings and discussions.

9.1 Site Monitoring Plan

A site monitoring plan will be designed for each study to supplement the BPCA project-wide clinical monitoring plan based on protocol risk assessments.

REDACTED

10 STATISTICAL CONSIDERATIONS

10.1 Study Outcome Measures

10.1.1 Primary Outcome Measures

- 1) PK parameters after multiple IV doses of clindamycin:
 - Clearance (Cl)
 - Volume of distribution (Vd)
 - Area under the curve (AUC_{τ})

10.1.2 Secondary Outcome Measures

- 1) PK results of patients transitioned to oral clindamycin:
 - Oral apparent clearance (Cl/F)
 - Oral apparent volume of distribution (V/F)
- 2) Safety: Adverse events will be collected during and after study drug administration.

10.2 Sample Size Considerations

It is anticipated that 12 children will be enrolled and treated in each of the IV groups for each age strata, leading to a total sample size of 24 participants. A sample size of 24 participants will provide adequate precision in the Cl/F PK parameter estimate. Assuming an inter-individual 40% coefficient of variation in the population Cl parameter estimate after weight-based allometric scaling, a sample size of 24 participants would provide a margin of error of $\pm 16\%$ in the 95% confidence interval of the Cl estimate.

10.3 Analysis Plan

Population for Analysis

All participants that receive at least 1 dose of study drug will be included in the safety analysis. All participants with at least 1 evaluable PK sample will be included in the PK analysis plan. If participants have < 3 timed PK samples, additional participants may be enrolled to ensure appropriate analysis.

Statistical Methodology

Descriptive statistics, such as number of observations, mean, median, 95% confidence interval, standard deviation, standard error, minimum, and maximum, will be presented by cohort for continuous variables (such as age, weight, and BMI). Other descriptive statistics, such as counts, proportions, and/or percentages, will be presented by cohort group to summarize discrete variables (such as race and sex).

Demographics and Baseline Characteristics

The number of participants completed and discontinued early from study, and the reasons for discontinuation, will be summarized. Demographic and baseline characteristics will also be summarized. Variables include race, ethnicity, age, sex, and selected clinical variables recorded prior to initiation of study drug. Study drug administration will be summarized by age and BMI cohorts.

Laboratory data, such as hematology and serum chemistry data, will be tabulated by age and BMI cohorts. Continuous laboratory measurements will be described using univariate descriptive statistics (mean, median, etc.); observed values and changes from baseline will be summarized. Lab tests reflective of liver toxicity (e.g., ALT, AST) will be further summarized in terms of the most extreme values and largest changes from baseline (in the appropriate direction) observed from start of study drug through the end of therapy.

Interim PK Analyses

An interim PK analysis of each age cohort will be performed after approximately 4 participants have been enrolled into that cohort. If an interim analysis suggests that PK data is required on more than 12 participants in that age cohort to evaluate the PK of clindamycin in this population, approximately 4 additional participants will be enrolled into that age group for a total of 16 participants.

PK Analysis

Population PK analysis using non-linear mixed effects modeling (NONMEM VII software) will be used to estimate population PK parameters and their variance. The influence of covariates (i.e., TBW, BMI, lean body weight, adjusted body weight, IBW, etc.) on PK parameters will be explored. Post-hoc Bayesian individual PK parameters will then be estimated for each participant. The plasma concentrations-time profiles of clindamycin will be presented in figure form by participant and cohort (age and weight/BMI). Descriptive statistics will be presented for continuous and categorical variables. A detailed description of PK/PD analyses can be found in the PK analysis plan. We will compare PK parameters in this study of obese children to non-obese children.

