5.2.1 Duration of Study Participation

Duration of therapy will be up to 14 days for children who receive the first dose of IV clindamycin as the study drug. The total duration of therapy with clindamycin will be determined by the treating physician for those children who are receiving clindamycin as part of routine care; however, only 14 days of therapy will be considered as study drug. Study follow-up will occur 3 days (+/- 1 day) after the last dose of study drug. Patients who are receiving antimicrobial agents other than clindamycin may enroll in this study and receive up to 3 doses of IV clindamycin and 4 doses of oral clindamycin in addition to their standard of care therapy. Participants who transition to oral clindamycin may return as outpatients to complete the PK portion of the study.

Total duration of study participation will be up to 18 days. This will comprise a 1-day screening period; a maximum 14-day treatment period; and a 3-day post-study observation period to monitor for serious adverse events. The 3-day post-treatment visit may be a phone follow-up. Patients may continue clindamycin per their physician's recommendation after they have completed participation in this (maximum of) 18-day study.

Figure 2. Timeline

* Minimum of 1 dose of IV clindamycin before IV PK period (see **Section 6.6.2** for further details).

** Minimum of 3 doses of PO clindamycin before PO PK period.

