6.5 Follow-up Safety Phone Call

Assessments/Procedures (Day 3 Post Treatment): This visit will be a phone follow-up unless the participant is still hospitalized, in which case an in-person visit or chart review may be performed. This assessment will occur 3 days (+/- 1 day) after the last dose of study drug (i.e., end of therapy or early withdrawal/discontinuation). The following information will be obtained:

1. Adverse events (see **Section 8.2.1**)
2. Concomitant medications of interest (**Appendix II**)
3. Results for laboratory tests of interest (see **Section 6.6.1**)

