6.6 Laboratory Evaluations

6.6.1 Clinical Laboratory Evaluations

Laboratory testing (**Table 2**) will be collected on all participants and be performed in the local laboratory at each site. Laboratory values will be collected within 72 hours prior to the first dose of study drug through 3 days (+/- 1 day) after the last dose of study drug. If multiple values for a laboratory are obtained in the 72 hours prior to start of first study dose, record the value closest to the start of first study dose. Laboratory values performed as part of routine care within 72 hours prior to the first dose of study drug may be used for baseline laboratory tests. Laboratory values will also be obtained at the end of therapy. Laboratory values obtained within ± 24 hours of discontinuation of study drug or within ± 24 hours of completion of 14 days of study drug (if participant is continuing clindamycin beyond 14 days) may be used as end-of-treatment laboratory values. If the baseline and end of therapy laboratory tests have not been performed as part of routine care, they will be performed for the study per the protocol schedule. The serum pregnancy test will also be performed at the local laboratory. Alpha (α)-1-glycoprotein will be measured from one of the PK samples by the central laboratory once during the study using an ELISA kit (central laboratory). Sites do not need to collect an extra sample to measure α -1-glycoprotein.

Table 2. Laboratory Evaluations

Hematology	Serum Biochemistry
Hemoglobin	Sodium
Hematocrit	Potassium
Platelets	Chloride
White blood cells	Bicarbonate
	Total calcium
	Glucose
	Creatinine
	Blood urea nitrogen
	Total protein
	Albumin
	Aspartate aminotransferase
	Alanine aminotransferase
	Bilirubin

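### The ALT/AST extremes in 10.3 stop at end of therapy, so routine-care values drawn from about 24 h up to 48–96 h after the last study dose are recorded but left out

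*Supplement*

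**What the plan says.** All references are to the latest protocol version in the supplement.

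- **Analysis window.** The laboratory paragraph of 10.3 first promises a general tabulation of observed values and changes from baseline, with no stated end date. It then adds a further summary for liver tests, naming ALT and AST as examples: the most extreme values and the "largest changes from baseline (in the appropriate direction) observed from start of study drug through the end of therapy".
- **Collection window.** Section 6.6.1 states: "Laboratory values will be collected within 72 hours prior to the first dose of study drug through 3 days (+/- 1 day) after the last dose". Table 2 in that section lists "Alanine aminotransferase", along with aspartate aminotransferase and bilirubin.
- **Follow-up.** Section 6.5 says of the follow-up contact: "This assessment will occur 3 days (+/- 1 day) after the last dose of study drug". The data to be obtained there include "Results for laboratory tests of interest". Table 1 marks the follow-up column for laboratory tests only where they were done in routine care.
- **End-of-treatment allowance.** Section 6.6.1 accepts as end-of-treatment values "Laboratory values obtained within ± 24 hours of discontinuation of study drug or within ± 24 hours of completion of 14 days of study drug"; the latter applies to children who continue clindamycin beyond that point.
- **Adverse events.** Section 8.2 collects adverse events from consent until 3 days after the end of clindamycin therapy. Section 8.2.1 counts any clinically significant laboratory change as an adverse event.

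**The concern.** The plan gathers laboratory data over one window and searches for liver-test peaks over a shorter one, without giving a reason. A transaminase value drawn two or three days after the last study dose would reach the database and then be passed over by the one display designed to show how high these tests went. The reported maximum or largest change could then be lower than the largest value actually recorded.

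The safety outputs could also disagree. If a child has a clinically significant ALT rise on day 2 or 3 after treatment, the adverse event table would list it, while the liver-extremes table would omit the value behind it.

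Safety is a secondary aim, and section 2.3.1 names the liver among the organ systems affected by clindamycin. With 24–32 children and few laboratory values each, a single omitted value can determine what the maximum is.

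**Working it through.** The plan gives no figure to reproduce here. The check compares the windows and measures the uncovered interval, with time counted from the last dose of study drug.

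**Inputs**

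| Item | Value | Source |
|---|---|---|
| End of liver-extremes window | end of therapy | 10.3 |
| End of laboratory collection | 3 days ±1 day | 6.5, 6.6.1 |
| End-of-treatment allowance | up to +24 h | 6.6.1 |
| End of adverse event capture | 3 days | 8.2, 8.2.3 |
| Condition on follow-up laboratory tests | routine care only | Table 1 |

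**Step 1. End of laboratory collection, in hours.** Earliest 2 × 24 = 48 h; nominal 3 × 24 = 72 h; latest 4 × 24 = 96 h.

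**Step 2. Gap if the +24 h allowance counts as end of therapy.** Gap = end of collection − 24 h.
- Earliest: 48 − 24 = 24 h
- Nominal: 72 − 24 = 48 h
- Latest: 96 − 24 = 72 h

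**Step 3. Gap if 10.3 is read strictly, with no allowance.** The gap equals the end of collection: 48, 72 or 96 h. Section 10.3 does not say which reading applies. The first is the natural one, because section 6.6.1 itself treats those draws as end-of-treatment values.

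**Step 4. Overlap with adverse event capture.** Adverse events are captured to 3 × 24 = 72 h. From 24 h to 72 h, that is 72 − 24 = 48 h, a rise could be reported as an adverse event while its value is missing from the extremes. When follow-up is at its latest, the final 96 − 72 = 24 h lies beyond both the extremes window and the capture of newly starting events.

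**Step 5. Children treated beyond 14 days.** Section 5.2.1 counts only 14 days as study drug, and Table 1 labels end of therapy as day 14. On that reading, the follow-up values of a child who continues clindamycin are drawn while the child is still exposed, and the extremes rule omits them too. If end of therapy meant the end of all clindamycin, they would fall inside the window; section 10.3 does not settle this.

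**Step 6. Is there a text that closes the gap?** No section extends the liver extremes to follow-up or explains the earlier cut-off. The general tabulation in 10.3 has no stated cut-off, so it may include late values, but it is not a summary of peaks.

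**The case against.** **Follow-up draws are not required.** Section 6.6.2 confines study-driven laboratory draws to baseline and end of study, and follow-up is normally a phone call. Many discharged children will have no late value to omit. This stands: it limits the size of the problem and makes it impossible to count.

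**Late rises are not lost altogether.** The general tabulation has no end date, and a clinically significant rise becomes an adverse event. This also stands, but neither output reports the maximum or the largest change.

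**Stopping at end of therapy keeps ascertainment even.** Late values come only from routine care, plausibly in children who are still in hospital, so including them could make the maximum depend on who was tested. This does not carry the point. Values between baseline and end of therapy also come only from routine care, so the maximum is already unevenly ascertained, and a flag for on- or post-therapy values deals with the remainder.

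**Laboratory windowing is usually left to a separate analysis plan.** True of details that a protocol leaves open. Here, however, the protocol states a cut-off, so the matter is a stated rule and not a missing one.

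**Stronger readings.** A reader might infer that every rise after the last dose is excluded. The documents do not support that: values up to +24 h may serve as end-of-treatment values. A reader might also infer that in short courses most of the informative values are lost, since a child on other antimicrobials may "receive up to 3 doses of IV clindamycin and 4 doses of oral clindamycin in addition to their standard of care therapy". Three IV doses every 8 h span only 2 × 8 = 16 h. But hours are not data, the required end-of-treatment panel still counts, and with the permitted oral doses seven doses every 8 h span 6 × 8 = 48 h. No share of lost values can be derived.

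**Conclusion.** The point holds in a limited form. The liver-extremes summary ends earlier than laboratory collection, and the rule drops recorded ALT/AST values from about 24 h to 48–96 h after the last study dose, nominally a 48 h gap. If the +24 h allowance does not apply, the omitted interval is the full 48–96 h.

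This rests on two assumptions: that end-of-treatment draws up to +24 h count as end of therapy, and that end of therapy means day 14 of study drug for children who continue clindamycin, as Table 1 suggests. The number of children affected is unknown and could be small. The summary is descriptive and serves a secondary aim; the primary PK outcomes, the sample size and the halting rule are unaffected. The weight is minor to moderate, and the change is worth making because it costs almost nothing.

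**What to change.** In the liver-test sentence of 10.3, replace the end-of-therapy cut-off with the 3-day (±1 day) post-treatment assessment, so that the extremes cover every laboratory value recorded after the first study dose. Flag each extreme value as on-therapy or post-therapy. State how the flag treats draws within 24 h after the last study dose and draws in children who continue clindamycin after day 14. Reporting the on-therapy extreme alongside the overall one would preserve the present summary.

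The cost is one phrase in the analysis section and one derived flag in the tables. No further blood draws, visits or data fields are needed, because section 6.6.1 already has the values recorded with their follow-up window.

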11 PARTICIPANT CONFIDENTIALITY

The principal investigator will ensure that the use and disclosure of protected health information obtained during this research study complies with the Health Insurance Portability and Accountability Act (HIPAA) Privacy Rule. The rule provides U.S. federal protection for the privacy of protected health information by implementing standards to protect and guard against the misuse of individually identifiable health information of participants participating in clinical trials. "Authorization" is required from each research participant (i.e., specific permission granted by an individual to a covered entity for the use or disclosure of an individual's protected health information). A valid authorization must meet the implementation specifications under the HIPAA Privacy Rule. Authorization will be combined in the informed consent document (approved by the IRB).

Participant confidentiality is held strictly in trust by the participating investigators, their staff, the sponsor(s), and their agents. This confidentiality is extended to cover testing of biological samples, in addition to the clinical information relating to participating participants.

The study protocol, documentation, data, and all other information generated will be held in strict confidence. No information concerning the study or the data will be released to any unauthorized third party without prior written approval of the sponsor.

The clinical study site will permit access to all documents and records that may require inspection by the sponsor or its authorized representatives, including but not limited to, medical records (office, clinic, or hospital) and pharmacy records for the participants in this study.

12 INFORMED CONSENT PROCESS

Informed consent is a process that is initiated prior to the individual's agreeing to participate in the study and continuing throughout the individual's study participation. Extensive discussion of risks and possible benefits of participation in this study will be provided to the participants' families. Consent forms describing in detail the study procedures and risks are given to the participant's legal guardian, and written documentation of informed consent is required prior to enrolling in the study. Consent forms will be IRB-approved, and the participant's legal guardian will be asked to read and review the document. Upon reviewing the document, the investigator will explain the research study to the participant's legal guardian and answer any questions that may arise. The participant's legal guardian will provide informed consent prior to the participant being enrolled in the study. The participant's legal guardian may withdraw consent at any time throughout the course of the study. A copy of the informed consent document will be given to the participant's legal guardian for their records. The rights and welfare of the participant will be protected by emphasizing to their legal guardian that the quality of their medical care will not be adversely affected if they decline to participate in this study.

The IND sponsor or designee will provide the investigator, in writing, any new information that bears significantly on the participant's risk to receive the investigational product. This new information will be communicated by the investigator to participant's legal guardian who consented to participate in the trial in accordance with IRB requirements. The informed consent document will be updated, and participant's legal guardian will be re-consented, if necessary.

Site staff may employ IRB-approved recruitment efforts prior to the participant consenting; however, before any protocol-specific procedures are performed to determine protocol eligibility, an informed consent must be obtained.

By signing the informed consent form, the participant's legal guardian agrees that the participant will complete all evaluations required by the trial, unless the participant is withdrawn voluntarily or is terminated from the trial for any reason.

12.1 Assent Process (e.g., Minor)

When a study includes participants who may be enrolled in the study only with the consent of the participant's legally acceptable representative (e.g., minors), the participant should be informed about the study to the extent compatible with the participant's understanding. If capable, the participant should assent and sign and personally date the IRB-approved written assent form (if applicable based on local IRB guidelines). The assent form describes (in simplified terms) the details of the study, study procedures, and risks. Assent forms do not substitute for the consent form signed by the participant's legal guardian. Consult with the institution's policies regarding enrollment of participants who are unable to provide informed consent for themselves.

13 SOURCE DOCUMENTS AND ACCESS TO SOURCE DATA/DOCUMENTS

A CRF will be used to record participant data. The CRF will be used for the recording of all historical participant information and study data as specified by this protocol. The CRF must be completed by designated and trained study personnel. The CRF will be signed by the principal investigator. Data collection forms will be derived from the CRFs and provided by the DCC.

According to ICH E6, source data are defined as all information in original records and certified copies of original records of clinical findings, observations, or other activities in a clinical trial necessary for the reconstruction and evaluation of the trial. Source data are contained in source documents (original records or certified copies). Source documents are defined as original documents, data, and records (e.g., hospital records, clinical and office charts, laboratory notes, memoranda, participants' diaries or evaluation checklists, pharmacy dispensing records, recorded data from automated instruments, copies or transcriptions certified after verification as being accurate and complete, microfiches, photographic negatives, microfilm or magnetic media, x-rays, participant files, and records kept at the pharmacy, at the laboratories, and at medico-technical departments involved in the clinical trial).

It will be the responsibility of the investigator(s) to ensure that the study file (regulatory binder) at the site is maintained. The study file will contain, but will not be limited to:

- Current package inserts and all previous versions
- Final study protocol
- Protocol amendments (if applicable)
- MOP (if applicable)
- Informed consent form (blank)
- Signed informed consent forms
- Revised informed consent forms and/or all addenda (blank)
- DHHS number for IRB or other documentation of IRB compliance with FDA regulations (if applicable)
- Documentation of IRB approval of protocol, consent form, any protocol amendments, and any consent form revisions.
- Annual IRB updates and approvals
- All correspondence between the investigator and IRB

Each participating site will maintain appropriate medical and research records for this trial, in compliance with ICH E6, Section 4.9, and regulatory and institutional requirements for the protection of confidentiality of participants. Each site will permit authorized representatives of the sponsor, its designees, and appropriate regulatory agencies to examine (and, when required by applicable law, to copy) clinical records for the purposes of quality assurance reviews, audits, and evaluation of the study safety and progress. These representatives will be permitted access to all source data, which include, but are not limited to, hospital records, clinical and office charts, laboratory notes, memoranda, participants' memory aid or evaluation checklists,

pharmacy dispensing records, recorded data from automated instruments, copies or transcriptions certified after verification as being accurate and complete, microfiches, photographic negatives, microfilm or magnetic media, x-rays, and participant files and records kept at the pharmacy, at the laboratories, and at medico-technical departments involved in the clinical trial.

REDACTED

